6.6 Schedule of Evaluations

Table 1: Schedule of Evaluations

Visit Number	0	1	2	3	4	5
Time (Weeks [w]/Months [m])	-1m to 0	0	6w	6m	12m	18m
Window Period	-	-	±1w	±1m	±1m	±1m
Visit Type	Online + Phone	Clinic*	Phone	Clinic*	Phone	Clinic*
Remote / Electronic Informed Consent	X					
In-person Written Informed Consent		X				
SPHERE Questionnaire	X	X				
Blind MoCA	X					
Eligibility – Inclusion/Exclusion Criteria	X	X				
Medical History, Demographics & Socio-Economic Status		X				
Pregnancy Test – where required		X				
Lifestyle – Smoking, Diet, Alcohol		X		X		X
History of Health Service Use for COVID-19/Visits to Medical Professionals		X		X		X
Anthropometrics – Height & Weight		X				X
Blood Pressure, Heart Rate		X		X		X
Fasting Bloods	Haematology/Electrolytes/Renal/Liver Function – full blood count, Na, K, urea, nitrogen, creatinine, eGFR, ALT, AST, CK		X			X
	Glucose/Lipids/Inflammation – glucose, total cholesterol, LDL, HDL, triglycerides, CRP		X			X
	Neurodegenerative Biomarkers – 220 participants		X			X
Cognitive Assessments – SDMT, RAVLT-D, OTMT-A, OTMT-B, D-KEF-CWIT, SF		X		X		X
Health Assessments – PHQ-9, GAD-7, PSQI, EQ-5D-5L		X		X		X
Actigraphy plus Sleep Diary – 7-day Capture		X		X		X
Brain MRI – 220 participants		X				X
Dispense Study Medication – treatment arm only		X		X	X	
Study Medication Adherence & Accountability – treatment arm only			X	X	X	X
Concomitant Medications		X	X	X	X	X
SAEs/AESIs			X	X	X	X

*For participants who cannot attend the clinic, efforts will be made for visit assessments to be conducted remotely via tele-/videoconference.

ALT – Alanine Aminotransferase

AST – Aspartate Aminotransferase

CK – Creatine Kinase

CRP – C-Reactive Protein

D-KEF-CWIT – Delis-Kaplan Executive Functioning System “Stroop” Colour-Word Interference Test

GAD-7 – Generalised Anxiety Disorder-7

HDL – High-Density Lipoprotein

LDL – Low-Density Lipoprotein

MoCA – Montreal Cognitive Assessment

MRI – Magnetic Resonance Imaging

PSQI – Pittsburgh Sleep Quality Index

RAVLT-D – Rey Auditory Verbal Learning Test – Delayed Recall

SDMT – Symbol Digit Modalities Test

SF – Semantic Fluency

SPHERE – Somatic and Psychological Health Report

eGFR – estimated Glomerular Filtration Rate
EQ-5D-5L – EuroQoL 5-Dimensional 5- Level Questionnaire

OTMT – Oral Trail Making Tests A & B
PHQ-9 – Patient Health Questionnaire-9

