- Actigraphy watches and a sleep diary will be mailed to all participants for recording of their physical activity and sleep over a 7-day period in the next 2 weeks, and then returned by courier to a central office for downloading of data.
- *Brain MRI (sub-study group: 220 participants)*
- Randomisation – if eligible
 - After confirmation of eligibility, participants are randomised to receive standard care or study medication (atorvastatin 40mg) according a stratification scheme that involves (see Section 11.2) country, time since the acute COVID-19 illness, age, current anosmia, and participation in the MRI/biomarker substudy .
 - Participants will only be informed of their treatment allocation once they have completed all baseline assessments, in order to reduce the risk of differential withdrawal between the two arms.
- Dispense study medication – treatment arm only
 - Study medication will be dispensed in person or via courier in each country; if the latter, an SMS message will be sent by the participant to the regional research office to confirm receipt of study medication. If no message is received, the office will contact the participant by telephone for confirmation.
- Record of concomitant medications

Visit 1 will take approximately 3-4 hours.

All women of child-bearing potential must have a confirmed menstrual period and a negative highly sensitive pregnancy test 7 days or fewer before starting run-in medication and must use a highly effective method of contraception throughout their participation in the study. Highly effective contraceptive methods include hormonal contraception (oral, intravaginal, transdermal, injectable, implantable) or intrauterine device. These methods are not required in the case of bilateral tubal occlusion, vasectomised partner or true sexual abstinence (i.e. within line of the person's preferred and usual lifestyle).

A subset of participants (n=220) will be invited to participate in a sub-study involving:

- the collection and storage of blood for future neurodegenerative biomarker studies, and
- Brain MRI scanning (45 mins).

These additional assessments will be undertaken either the same day or within the next 7-10 days of the baseline clinical assessment, according to booking availability. See Section 6.10 for further information.

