11.2 Assignment of Intervention

Participants will be registered and randomised via a secure web-based database. The randomisation will be stratified by the following factors: (i) country; (ii) time (<6 vs. ≥ 6 months since acute COVID-19 illness), (iii) age (<60 vs. ≥ 60 years), (iv) Current anosmia that has occurred in relation to COVID-19, and (v) participation in the MRI/biomarker substudy.

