11.3 Statistical Analysis

The study follows the ITT principle for analysis. Baseline characteristics will be summarised by treatment group. The primary endpoint of change on the SDMT score will be summarised by means (SD)/medians (interquartile range), with the treatment effect tested by a Wilcoxon test. Continuous endpoints will be summarised by means/medians. The primary analysis will be through logistic regression models adjusted for region, age and sex. A sensitivity analysis will be undertaken with adjustment for baseline imbalances and clinically meaningful confounders. Descriptive statistics will be provided for safety data, where SAEs and treatment discontinuation will be tabulated using standard terminology. Heterogeneity of treatment on the primary endpoint will be assessed in pre-defined subgroups, such as age, time since COVID-19 diagnosis, baseline CRP levels, ethnicity, and prior cardiovascular risk. Analyses will be specified a priori in a full statistical analysis plan. A modelled cost-utility analysis using trial data (HRQoL, captured by EQ-5D-5L; drug costs; and health service utilisation costs, including AEs) will be conducted comparing use of atorvastatin and

standard care. A 5-year time horizon will be undertaken, with analyses conducted in line with accepted Australian standards for use of economic evaluation in decision-making.

12 Outcomes

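### The primary model is logistic for a continuous endpoint and omits baseline SDMT and three of the five randomisation factors; one linear baseline-adjusted model would gain precision at almost no cost

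*Protocol*

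**What the plan says.** Section 11.3 defines the outcome as "The primary endpoint of change on the SDMT score", "with the treatment effect tested by a Wilcoxon test". Two sentences later it says that the primary analysis will use "logistic regression models adjusted for region, age and sex". No dichotomised or ordinal SDMT outcome is defined in the protocol; section 6.8.3 scores the test as a count of correct symbols. Further adjustment appears only as a sensitivity analysis for baseline imbalances and confounders.

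Section 11.2 fixes the randomisation scheme: "The randomisation will be stratified by the following factors: (i) country", followed by time since illness and age (below 60 against 60 and over), and ending with "iv) Current anosmia that has occurred in relation to COVID-19, and (v) participation in the MRI/biomarker substudy". Section 6.7.2 gives the same five: "country, time since the acute COVID-19 illness, age, current anosmia, and participation in the MRI/biomarker substudy". Section 11.3 also proposes subgroup analyses by factors "such as age, time since COVID-19 diagnosis, baseline CRP levels", so time since infection is already regarded as potentially important.

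The schedule in section 6.6 lists "Cognitive Assessments – SDMT, RAVLT-D, OTMT-A, OTMT-B, D-KEF-CWIT, SF" at Visit 1, month 6 and month 18, so a baseline SDMT score is planned for every participant.

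**The concern.** The covariate list does not match the design. If region means country, the model covers country and age, adds sex (not a stratifier), and leaves out time since illness, anosmia and sub-study participation. If region means something else, four of the five factors are missing. Baseline SDMT, likely to be the strongest predictor of follow-up SDMT, is not in the model.

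Two separate costs follow:

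- **Baseline SDMT omitted.** Precision and power are lost. The randomised comparison stays unbiased and its standard error stays valid.
- **Stratification factors omitted.** To the extent that these factors are prognostic, stratified allocation balances them, but the model still counts their variance as noise. The reported standard error is then conservative: intervals are too wide and true type I error is below 5%.

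The covariates cannot be corrected alone, because a logistic model cannot be fitted to an undichotomised change score. Model type and covariates have to be settled together.

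**Working it through.** **Inputs.** Section 11.1: N = 410, equal groups, effect 0.3 SD, alpha 0.05, power 90%, 5% dropout, 5% non-compliance, SDMT SD 13 at baseline (healthy controls). Section 6.8.3: test-retest correlation 0.89 over 1 week. Assumptions: two-sided test; non-compliance dilutes the effect; SD 13 also holds at 18 months; the baseline-to-18-month correlation r is not given, so a range is shown.

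**The plan's own figure.** An unadjusted two-sided comparison at 0.3 SD with 90% power needs 234 per arm, or 468, before losses. With 410, power is 85.9% with no losses, 84.1% after 5% dropout, and 80.3% with dropout and dilution (normal approximation). The stated 90% is therefore not reproduced on this reading. A one-sided test with dropout only gives 403. A two-sided baseline-adjusted analysis with both losses gives 411 if r = 0.5, but the protocol states neither of these.

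**Baseline adjustment (linear analysis).** n per arm = 410 × 0.95 / 2 = 194.75. Diluted effect = 0.3 × 0.95 = 0.285 SD, or 3.7 points at SD 13.

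- Change score: SE = 13 × √(2(1−r)) × √(2/n)
- Baseline-adjusted (ANCOVA): SE = 13 × √(1−r²) × √(2/n)
- Variance ratio, change to ANCOVA: 2/(1+r)

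| r | 2/(1+r) | SE change | SE ANCOVA |
|---|---|---|---|
| 0.5 | 1.333 | 1.317 | 1.141 |
| 0.7 | 1.176 | 1.020 | 0.941 |
| 0.8 | 1.111 | 0.833 | 0.790 |
| 0.89 | 1.058 | 0.618 | 0.601 |

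Power (noncentral t; Wilcoxon by its efficiency 3/π) depends on which SD the 0.3 refers to:

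| r | Cross-sectional SD: change / Wilcoxon / ANCOVA | SD of change: change / Wilcoxon / ANCOVA |
|---|---|---|
| 0.5 | 80.1 / 78.3 / 90.0% | 80.1 / 78.3 / 90.0% |
| 0.7 | 95.2 / 94.3 / 97.6% | 80.1 / 78.3 / 86.1% |
| 0.8 | 99.3 / 99.1 / 99.7% | 80.1 / 78.3 / 84.1% |
| 0.89 | all above 99.9% | 80.1 / 78.3 / 82.3% |

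A simulation (390 participants, 1,500 trials per r, cross-sectional SD) agrees: at r = 0.5, Wilcoxon 78%, linear change model 80%, with baseline added 89%. A logistic model on an assumed median split of change gave 61% at r = 0.5 and 82% at r = 0.7. That cut is not in the protocol, so these two figures are illustrative only.

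**Omitted stratification factors.** The protocol gives no prognostic strength. Let R² be the share of outcome variance explained by the three missing factors. If allocation balances them, the reported SE is too large by 1/√(1−R²) − 1, and true type I error is 2 × [1 − Φ(1.96/√(1−R²))].

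| R² | SE too large by | Type I error |
|---|---|---|
| 1% | 0.5% | 4.9% |
| 5% | 2.6% | 4.4% |
| 10% | 5.4% | 3.9% |
| 15% | 8.5% | 3.4% |

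A simulation of 4,000 null trials per setting (N = 390, 2 × 2⁴ = 32 strata, permuted blocks of 4 assumed, linear model) gave type I error of 0.039, 0.043 and 0.036 with the factors omitted, at R² = 5, 10 and 15%. With them included it was 0.045, 0.054 and 0.053. The Monte Carlo SE is 0.0035, so the direction is clear but the gradient across R² is not resolved.

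**Cost of the extra terms.** With two countries, baseline SDMT, five randomisation factors and sex use 1 + 5 + 1 = 7 degrees of freedom out of about 390. In simulation at r = 0.5, adding three factors with no prognostic value raised the mean SE from 0.0882 to 0.0885 (0.3%) and moved power from 88.9% to 88.8%.

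**The case against.** The strongest reply is that the covariates are the lesser problem. The outright contradiction in section 11.3 is a logistic model and a Wilcoxon test both claiming a continuous endpoint, and until that is settled the right covariates cannot be judged. That stands as a point of emphasis, and it is why the fix deals with both together. An undefined cut point and a free choice between two analyses also carry a risk that the covariate omissions do not.

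Second, the linear figures do not measure the loss from the logistic model as written. That is correct. Its loss cannot be computed without a definition of the binary outcome.

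Third, the gain is assumed. A change score already uses baseline, and at the only correlation in the document, 0.89, the gain is just 6%. The rise from 80% to 90% needs r = 0.5, which appears nowhere. This too is correct, but 0.89 is a 1-week value and the follow-up is 18 months. The strength of the strata and the block size are likewise assumed.

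Fourth, section 11.3 defers to a full SAP and allows adjustment for clinically meaningful confounders. That adjustment is confined to a sensitivity analysis. The protocol itself fixes the model type and the covariates, so an SAP that chose better would have to depart from it.

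**Conclusion.** The concern holds. The stated primary model does not suit the endpoint, and its covariate list leaves out baseline SDMT and, with region read as country, three of the five randomisation factors. The harm is lost efficiency: neither omission biases the estimate or creates a false-positive risk.

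Baseline adjustment is worth 6% to 33% more effective sample for r from 0.89 down to 0.5. That is 2 to 10 percentage points of power if 0.3 SD refers to change. If it refers to the cross-sectional SD, the gain is about 10 points at r = 0.5, about 2 at r = 0.7, and negligible above that. Conservatism from the omitted strata is trivial at R² = 1% and noticeable only towards 15%. The sizes rest on an unknown 18-month correlation and unknown prognostic strength, and apply to linear analysis only. The case for changing the plan does not depend on the upper end of either range, because the cost is close to nil.

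**What to change.** Name a single primary analysis in section 11.3: a linear model (ANCOVA, or MMRM using the 6- and 18-month visits) of SDMT at 18 months, with continuous baseline SDMT and the five factors of section 11.2 (country, time since illness, age, current anosmia, sub-study participation) as covariates. Sex may stay as an option. Report the adjusted mean difference with its 95% confidence interval. Remove the logistic model, and make the Wilcoxon test supportive or delete it. Keep the sensitivity analysis, but list its covariates in advance instead of choosing them from observed imbalance.

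The cost is two sentences in the protocol, carried into the SAP. Every variable is already collected at baseline or used at randomisation.

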12.1 Primary Outcome

The primary outcome is processing speed, assessed by the oral SDMT.

12.2 Key Secondary Outcome

The key secondary outcome is total white matter free water (dMRI) undertaken using data collected in standard procedures using multi-shell diffusion spectral imaging with fibre orientation and compartment modelling. SC members from Monash University have developed a novel computational framework to accurately characterise multi-shell diffusion spectral imaging signals from high b-values whilst retaining the capability of reliably resolving crossing fibres. Three compartments are used to associate brain microstructure to the diffusion signal: an intra-axonal compartment, an extra-axonal compartment, and a third compartment representing the fraction of trapped water molecules with essentially negligible diffusion.

12.3 Other Outcomes

Various other components of cognition; other health assessments and MRI markers of white matter hyperintensity volume, enlarged peri-vascular space volume, total grey matter volume, white matter microstructure (fractional anisotropy), basal ganglia iron load and total cerebral perfusion, and spectroscopy-derived glutathione as a marker of oxidative stress; cost-effectiveness compared to standard care.

12.4 Safety Outcomes

AEs, AESIs and SAEs.

13 Safety

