2.3.4 Data & Safety Monitoring Board

An independent Data & Safety Monitoring Board (DSMB) will be constituted. This committee will receive data and will have the power to recommend to the SC potential modifications to study conduct including early discontinuation of the study based on a risk/benefit assessment of the study data. The DSMB will also monitor the occurrence of serious adverse events (SAEs), adverse events (AEs) and adverse events of special interest (AESIs) throughout the study in order to monitor participant safety.

3 Protocol Synopsis

Main Sponsor: The George Institute for Global Health (TGI)	Trial Registration Number(s): STRONGER will be registered on Clinicaltrials.gov and ANZCTR
Title of Study: Statin Treatment for COVID-19 to Optimise Neurological recovery (STRONGER)	
Study Duration: 3 years	Clinical Phase: III
Objectives: To determine effectiveness of treatment with 40mg atorvastatin over 18 months on attenuating cognitive decline and neuroinflammatory biomarkers in adults with long COVID neurological symptoms.	
Number of planned participants: 410	
Study Design: Prospective, randomised, open-label, blinded endpoint (PROBE) study of atorvastatin 40mg on top of standard care, in patients with long COVID neurological symptoms.	
Study Treatment: 40mg atorvastatin + standard care or standard care alone	

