
Outcome Measures:
 
Primary – processing speed, assessed on the oral Symbol Digit Modalities Test (SDMT)
 
Key Secondary – white matter free water measured on diffusion MRI brain imaging
 
Other – other components of cognitive function; other health assessments; other MRI markers of cerebral white matter integrity, iron load, cerebral perfusion, and glutathione for oxidative stress; cost-effectiveness compared to standard care
 
Safety – any SAEs, AEs or AESI including diabetes mellitus, myalgia, myositis, and biochemical abnormalities
	

4 Introduction

COVID-19 Pandemic

By early 2021, the COVID-19 pandemic, caused by the severe acute respiratory syndrome coronavirus 2 (SARS-CoV-2), had affected approximately 100 million people and caused over 1.8 million deaths, since it emerged in Wuhan, China in late 2019. The epidemiological pattern and clinical spectrum, pathogenesis, and complications in those infected with SARS-CoV-2 and diagnosed with COVID-19 in the acute phase have now been relatively well-described,^{1,2} but there is uncertainty over its long-term health consequences. However, there is increasing recognition that many patients have persistent symptoms, in particular ongoing impairment of cardiorespiratory, mobility, cognitive and psychological function.³ Although post-acute syndrome is well-recognised in patients recovering from serious illness, particularly those requiring hospitalisation and admission to intensive care units, post-acute COVID-19 syndrome is not just observed in those who have had severe illness and were hospitalised. Studies have shown that up to three-quarters of patients report at least one symptom several months after onset of the infection. The most common symptoms of 'long COVID' are fatigue, muscle weakness, disturbed sleep, and anxiety/depression. Approximately 5-10% of people report neurological symptoms, such as 'brain fog', headaches, poor concentration, and dizziness.⁴⁻⁸

COVID-19 & The Brain

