6.7 Visit Summary

In-person visits will be supplemented with telephone interviews to check on a participant's ongoing health status, adherence to study medication, and any AEs/SAEs, as well as to provide support and appointment reminders. If participants are unable to attend in-person visits, Zoom based (or telephone) interviews will be undertaken to assess the various health measures, where possible.

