6.7.3 Visit 2 – 6 Weeks (\pm 1 Week) – Telephone

The following will be assessed at the 6-week phone call:

- Review of any SAE/AESIs since last visit
- Adherence to study medication (participant-reported) – treatment arm only
- Changes to concomitant medications

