13.2.2 AESI

The expected adverse reactions to the study medication that will be used in this study that are of special interest are listed below. To better assess participants' tolerability to the study medications, the following AESIs and whether they are new or ongoing from baseline, will be reported in the eCRF at specified visits, regardless of severity and seriousness:

- myalgia
- nausea
- elevation in blood glucose
- elevation in creatinine kinase
- abdominal pain
- new-onset diabetes mellitus
- rhabdomyolysis

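### All AEs are a declared safety outcome, but the visit schedule asks only for SAEs and AESIs, so other non-serious events would be captured inconsistently

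*Protocol*

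**What the plan says.** **Declared.** Section 12.4 gives the safety outcomes as "AEs, AESIs and SAEs". The outcome list in the synopsis (Section 3) reads "any SAEs, AEs or AESI including diabetes mellitus, myalgia, myositis, and biochemical abnormalities". Section 2.3.4 has the DSMB follow AEs as well as SAEs and AESIs throughout the study. Section 11.3 counts AEs among the costs in the cost-utility analysis.

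**Scheduled.** The Table 1 safety row is headed SAEs/AESIs and is marked at Visits 2 to 5. The safety item in Section 6.7.3 is "Review of any SAE/AESIs since last visit", and the lists for Visits 3, 4 and 5 carry the same item. Section 13.2.2 sends the listed AESIs to the eCRF at specified visits, whatever their severity. Section 13.2.5 gives a collection period for SAEs only. Section 13.2.3 adds that events leading to treatment discontinuation are documented, serious or not.

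**In conflict with the schedule.** The introduction to the visits in Section 6.7 says that telephone interviews check "adherence to study medication, and any AEs/SAEs".

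**The concern.** A declared outcome needs a collection procedure applied in the same way to every participant. Here sites have two instructions. The outcome sections, the DSMB section and Section 6.7 cover all AEs. The schedule and visit lists, which staff follow on the day, cover only SAEs and AESIs. One site might ask about any AE at each contact and another might ask only the scheduled question, and both could point to the protocol.

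Participants and treating staff know the allocation (Section 7.2). Events that no one is scheduled to ask about are recorded only if a participant volunteers them or a site chooses to ask, and either could differ by arm. The DSMB, the safety tables and the costing would then receive AE data of uncertain completeness. An SAP cannot repair this, because it cannot supply events that the visits never requested.

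**Working it through.** No arithmetic applies beyond counting, and the protocol states no figure to reproduce. The check sets the provisions side by side.

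| Provision | SAEs | Listed AESIs | Other non-serious AEs |
|---|---|---|---|
| 12.4 Safety outcomes | yes | yes | yes |
| Synopsis, safety outcomes | yes | yes | yes |
| 2.3.4 DSMB monitoring | yes | yes | yes |
| 6.7 Telephone interviews | yes | not named separately | yes |
| Table 1 safety row, Visits 2–5 | yes | yes | no |
| Lists for Visits 2, 3, 4 and 5 | yes | yes | no |
| 13.2.2 eCRF instruction | – | yes | – |
| 13.2.3 Events leading to discontinuation | yes | yes | only if treatment stops |
| 13.2.5 Reporting period | yes | no | no |

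1. **Coverage.** There are four scheduled follow-up contacts: 6 weeks, 6, 12 and 18 months. Other AEs appear in none of the four lists.
2. **Direct conflict.** Visits 2 and 4 are telephone contacts, so for two of the four the general instruction in Section 6.7 and the visit list differ. For the clinic visits (3 and 5), Section 6.7 gives no clear AE instruction.
3. **What remains.** Removing SAEs, AESIs and events that end treatment leaves non-serious, non-AESI events in participants who continue as before. These have no consistent collection rule and no reporting window.
4. **Arms.** The Table 1 safety row is not restricted by arm, and both arms have the same contacts. Adherence review and dispensing apply to the treatment arm only. The discontinuation route in Section 13.2.3 can arise only there too, since standard care has no study medication to stop. Uneven capture by arm is therefore possible, but the protocol gives nothing from which to estimate its size.
5. **AESI list against synopsis.** Section 13.2.2 has seven items: myalgia, nausea, raised blood glucose, raised CK (printed as "elevation in creatinine kinase"), abdominal pain, new-onset diabetes and rhabdomyolysis. The synopsis names diabetes, myalgia, myositis and biochemical abnormalities. Diabetes and myalgia match. Myositis is absent by name, although myalgia, raised CK and rhabdomyolysis cover part of it. The biochemical term matches two listed items (glucose and CK) but is not otherwise defined. ALT, AST and CK are named among the bloods at Visits 1 and 5.

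**The case against.** The strongest reply is that little is lost. The events that matter most for a marketed statin are SAEs, the listed AESIs and events that stop treatment, and all of these are collected. Section 6.7 shows an intention to ask about AEs, both arms have the same contacts, and Section 11.3 plans only descriptive safety statistics. The synopsis wording can also be read so that its examples attach to AEs and SAEs as well as AESIs, in which case it need not promise myositis as an AESI. These points stand, and they limit the size of the problem. They do not remove the conflict between the outcome sections and the schedule, and a descriptive table by arm still depends on even collection.

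A reader might go further and infer four things that the protocol does not support:

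- **The safety outcomes cannot be reported at all.** SAEs, listed AESIs and AEs leading to discontinuation can be.
- **The synopsis promises liver enzymes that the AESI list omits.** It refers to biochemical abnormalities and names no liver test. ALT and AST are scheduled bloods, so rises can be derived from the results.
- **Myositis and liver biochemistry have no eCRF field.** The eCRF is not shown, and Section 13.2.2 does not say that it holds nothing else.
- **AE reports will run higher on atorvastatin.** This is plausible in an open-label trial, but it is inference.

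**Conclusion.** The contradiction is real and should be resolved, in a limited form. Three provisions declare AEs an outcome or a DSMB responsibility, and a fourth (6.7) tells telephone contacts to check for them. Table 1 and all four follow-up visit lists leave them out, and no reporting period covers them. The affected class is non-serious events that are not AESIs and do not lead to discontinuation. For that class, a summary by arm would be incomplete and hard to interpret. The direction and size of any difference between arms cannot be stated from the protocol.

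The AESI mismatch is a smaller point: one named term, myositis, is in the synopsis but not in the list, and the biochemical item is undefined.

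This rests on the assumption that sites work from Table 1 and the visit lists. If a procedure manual or the eCRF, neither of which is shown, already requires AE review at every contact in both arms, the remaining defect is one of protocol wording.

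**What to change.** Choose one of two routes and apply it everywhere.

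- **Narrow the outcome.** Restrict Section 12.4, the synopsis, Section 2.3.4 and Section 6.7 to SAEs, AESIs and AEs leading to discontinuation, and bring the AE costing phrase in Section 11.3 into line. Changing 12.4 and the synopsis alone would leave 2.3.4 and 6.7 in conflict. This costs only wording; the downside is a narrower stated safety outcome. AEs leading to discontinuation should be described as information on the atorvastatin arm, not as a between-arm comparison.
- **Widen the collection.** Add AE review for both arms to Table 1 and to Visits 2 to 5, with a stated reporting period. Section 13.2.1 words an AE around a product administered, so say plainly that events under standard care count. This costs a little more data entry and should be in place early, because events not asked about at past visits cannot be reliably recovered.

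Under either route, make the synopsis and Section 13.2.2 agree on myositis, state which biochemical abnormalities are meant (ALT and AST are already measured), and correct the printed name of creatine kinase in Section 13.2.2.
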